784 routinely completed by ambulance staff after each case that they attend.

785

786 Source A will be the primary data source for the study. However, by triangulating data from all three sources it is
787 possible to reliably identify all, or nearly all, OHCA's where resuscitation is attempted during the study period. Whilst
788 it is possible for an eligible OHCA to be overlooked by this triangulation process, it would require that an arrest not be
789 reported to the research team by a participating paramedic, not be identified as an OHCA on the CAD and not be
790 picked up by the ambulance trust's routine identification and reporting system. We estimate that the chance of this
791 happening is very low, thereby ensuring an exceptionally high rate of eligible patient identification that reduces
792 selection bias to an absolute minimum.

793

794 **5.6.2 Out of hospital treatment phase (data collection by paramedics)**

795

796 After treating an eligible OHCA patient, the participating paramedic responsible for airway management will complete
797 a CRF to capture baseline and secondary outcome data. The CRF will be completed at the same time as routine
798 ambulance service paperwork: immediately after the patient has been handed over to the receiving hospital team or
799 resuscitation attempts have been discontinued at the scene. The CRF should then be returned as soon as possible
800 (preferably within 24 hours) to the coordinating research paramedic by a secure method chosen by each trust e.g. post,
801 secure fax or e-mail. Occasionally the participating paramedic will not complete the form immediately, in which case
802 they will be contacted by the research paramedic subsequently, and encouraged and supported to do so.

803

804 Even when this does not occur, relevant data can be extracted from the routine ambulance service record within 48
805 hours, allowing the patient to be followed up in order to obtain consent and collect primary and secondary outcome
806 data. Ambulance services reliably collect data regarding the individuals attending each patient and the time of staff
807 arrival: therefore for every eligible patient the attending ambulance paramedic(s), trial allocation and a range of
808 baseline data can be determined with near 100% accuracy.
809

810 **5.6.3 Hospital discharge (data collected by hospital staff)**

811

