1860 higher scores denoting higher Quality of Life (QoL)).

1861 Trial patients who did not survive to 30 days/hospital discharge will be assigned EQ-5D visual analogue scale
1862 and summary index scores of zero.

1863

1864 **5.4 Other variables**

New variable	Rules
POPULATION 0 and 1:	
Age	If date of birth ≠ missing: Age= (OHCA date – Date of birth) /365.25 If date of birth = missing: Age= approximate age (see section 4) Else missing
999 call to first crew arrival time (mins)	(First crew arrival date-incident date)*24*60 + (First crew arrival time-incident time)
POPULATION 1:	
Trial patient	If was resuscitation attempted=Yes and was incident attended by AIRWAYS-2 paramedic=Yes and did patient meet eligibility criteria=Yes, then = Yes

New variable	Rules
Survival status to hospital discharge	
If was resuscitation attempted=No or was incident attended by AIRWAYS-2 paramedic=No or did patient meet eligibility criteria=No, then = No
 
Else missing
 
If admitted to ED (Form D)=No, then = Died on scene
 
If admitted to ED=Yes, and survived to ICU admission (Form G)=No, then = Died prior to ICU admission
 
If admitted to ED=Yes, and survived to ICU admission=Yes, and survived to ICU discharge (Form G)=No, then = Died prior to ICU discharge
 
If admitted to ED=Yes, and survived to ICU admission=Yes, and survived to ICU discharge (Form G)=Yes, and transferred=Yes and level of care in transferred hospital (form G2)=Level 3 and survived to ICU discharge (Form G2)= No, then = Died prior to ICU discharge
 
If admitted to ED=Yes, and survived to ICU admission=Yes, and survived to ICU discharge=Yes and ((transferred = No) or (transferred=Yes and level of care admitted to is level 2 or 1) or (transferred=Yes and level of care admitted to is level 3 and survived to ICU discharge=Yes)) and (mRS (Form H2/I2)=6 or (mRS (Form H2/I2) ≠6 & has patient died since ICU discharge (but prior to hospital discharge) (Form W2) = Yes) or survived to hospital discharge (form H3/I3)=No), then = Died prior to hospital discharge
 
If admitted to ED=Yes, and survived to ICU admission=Yes, and survived to ICU discharge=Yes and ((transferred = No) or (transferred=Yes and level of care admitted to is level 2 or 1) or (transferred=Yes and level of care admitted to is level 3 and survived to ICU discharge=Yes)) and (mRS≠6 or survived to hospital discharge=Yes, then = Survived to 30 days/hospital discharge)

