Date of death	
If survival status=died on scene, then = Date resus stopped (Form E1)
 
If survival status=died prior to ICU admission, then = Date of death 1 (Form G)
 
If survival status=died prior to ICU discharge and survived to ICU discharge (Form G)=No, then = Date of death 2 (Form G)
 
If survival status=died prior to ICU discharge and survived to ICU discharge (Form G2)=No, then = Date of death 3 (Form G2)
 
If survival status=died prior to hospital discharge & consent status=active or passive, then = death date (Form H/I3)
 
If survival status=died prior to hospital discharge & consent status≠active & consent status≠passive, then = death2 date (Form W2)
 
If survival status=survived to 30 days/hospital discharge & has patient died since hospital discharge=Yes, then = death3 date (Form W2)
 
Else missing

Time of death	
If survival status=died on scene, then = Time resus stopped (Form E1)
 
If survival status=died prior to ICU admission, then = Time of death 1 (Form G)
 
If survival status=died prior to ICU discharge and survived to ICU discharge (Form G)=No, then = Time of death 2 (Form G)
 
If survival status=died prior to ICU discharge and survived to ICU discharge (Form G2)=No, then = Time of death 3 (Form G2)
 
If survival status=died prior to hospital discharge & consent status=active or passive, then = Time of death (Form H/I3)

New variable	Rules

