Time to death	
If survival status=died prior to hospital discharge & consent status≠active and status≠passive, then = 12 midnight
 
If survival status=survived to 30 days/hospital discharge & has patient died since hospital discharge=Yes, then = 12 midnight
 
(we do not collect time of death for patients who died after ICU discharge and do not consent to any follow-up or for patients who consent to active follow-up but died after hospital discharge)
 
Else missing
 
For patients who die prior to admission, in hospital, or during the follow up period:
 
(Date of death – Incident date (Form A))*24*60 + (Time of death – Incident time (Form A))
 
For patients who survive to 30 days/hospital discharge & consent to active follow-up and provides 6 month follow-up data (i.e. censored at 6 months post discharge for analysis)=
 
(6m follow-up date (Form K-Cover) - Incident date (Form A)) *24*60 + (12 midday - Incident time (Form A))
 
For patients who survive to 30 days/hospital discharge & consent to active follow-up and provides 3 month follow-up data but not 6 month follow-up data (i.e. censored at 3 months post discharge for analysis)=
 
(3m follow-up date (Form K-Cover) - Incident date (Form A)) *24*60 + (12 midday - Incident time (Form A))
 
For patients who survive to 30 days/hospital discharge & consent to passive follow-up or consented to active follow-up but do not provide any 3 or 6 month data (i.e. censored at hospital discharge for analysis)=
 
(Hospital discharge date (Form H/I3) - Incident date (Form A)) *24*60 + (Hospital discharge time (Form H/I3) - Incident time (Form A))
 
For patients who survive to (30 days or) hospital discharge & did not consent to active or passive follow-up (i.e. censored at ICU discharge for analysis) =
 
(ICU discharge date (Form G) - Incident date (Form A)) *24*60 + (ICU discharge time Form G) - Incident time (Form A))
 
Note – if time to death exceeds 183 days, then it will be censored at 183 days

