Time to death event/censor variable	
If (survival status≠survived to 30 days/hospital discharge & survival status≠missing) or has patient died since hospital discharge=Yes, then = 0
 
If survival status=survived to 30 days/hospital discharge & (has patient died since hospital discharge=No or missing), then = 1
 
Else missing
 
Note – if time to death exceeds 183 days, then it will be censored at 183 days

72 hour survival	
if time to death≥72 hours, then = Yes
 
if time to death<72 hours & time to death censor variable=0, then = No
 
if time to death<72 hours & time to death censor variable=1 & (mRS date-incident date) >3 & mRS at 30 days/discharge≠6, then = Yes
 
Else missing

Time to death: 0 to 72h	
if time to death≥72 hours, then = 72h
 
if time to death<72 hours & time to death censor variable=0 (patient died), then = time to death

New variable	Rules
	if time to death < 72 hours & time to death censor variable = 1 (censored) & ((30 day/discharge mRS date - incident date) > 3 & mRS at 30 days/discharge ≠ 6), then = 72h
	if time to death < 72 hours & time to death censor variable = 1 (censored) & ((30 day/discharge mRS date - incident date) ≤ 3 & mRS at 30 days/discharge ≠ 6), then = time to death
	Else missing
Time to death event/censor variable: 0 to 72h	if time to death ≥ 72 hours, then = 1 if time to death < 72 hours & time to death censor variable = 0 (patient died), then = 0 if time to death < 72 hours & time to death censor variable = 1 (censored), then = 1 Else missing
First crew arrival to first A2 paramedic arrival (mins)	(First A2 arrival date - First crew arrival date) * 24 * 60 + (First A2 arrival time - First crew arrival time)
Time of 999 call to first A2 paramedic arrival (mins)	(First A2 arrival date - Incident date) * 24 * 60 + (First A2 arrival time - Incident time)
Time between incident and discharge/30 day mRS measurement (days)	(mRS date - incident date) if measured face-to-face Else missing
Event witnessed by	if event witnessed by = non-ambulance staff (Form E1) or (event witnessed by = missing (Form E1) and event witnessed by = bystander (Form B)), then = bystander If event witnessed by = AIRWAYS-2 paramedic or ambulance staff (Form E1) or (event witnessed by = missing (Form E1) and event witnessed by = EMS (Form B)), then = EMS Else missing

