Utstein comparator group	if event witnessed by = bystander and presenting rhythm = VF or pulseless VT, then = Yes if (event witnessed by = bystander and presenting rhythm = Asystole OR PEA OR unknown) or event witnessed by = EMS, then = No Else missing
Protocol deviation 1: consciously enrolled but ineligible	if consciously enrolled = Yes AND trial patient = No, then = Yes if trial patient = Yes, then = No Else missing
Protocol deviation 2: wrong paramedic enrolling patient	if Paramedic AIRWAYS-2 ID (Form A) ≠ Paramedic AIRWAYS-2 ID (Form E1) and Paramedic AIRWAYS-2 ID (Form E1) ≠ missing and trial patient = Yes, then = Yes if Paramedic AIRWAYS-2 ID (Form A) = Paramedic AIRWAYS-2 ID (Form E1) and Paramedic AIRWAYS-2 ID (Form E1) ≠ missing and trial patient = Yes, then = No
Protocol deviation 2: wrong paramedic enrolling patient resulting in allocation crossover	if protocol deviation 2 = Yes and allocation of enrolling paramedic ≠ allocation of first A2 paramedic on scene, then = Yes if protocol deviation 2 = Yes and allocation of enrolling paramedic = allocation of first A2 paramedic on scene, then = No Else missing
Protocol deviation 3:	if 'If no [airways management attempt completed on CRF E2], why?' = Further airway management commenced once A2 paramedic arrived but not carried out by enrolling A2 paramedic and trial patient = Yes, then = Yes

New variable	Rules
	if 'has at least one airway management attempt recorded on CRF E2?' ≠ missing and 'If no [airways management attempt completed on CRF E2], why?' ≠ Further airway management commenced once A2 paramedic arrived but not carried out by enrolling A2 paramedic and trial patient = Yes, then = No Else missing
Protocol deviation 4	if (Paramedic allocated to i-gel and first advanced airways management attempt is intubation or other SGA) or (Paramedic allocated to intubation and first advanced airways management attempt is i-gel or other SGA and paramedic is not a solo responder), then = Yes if first advanced airway management attempt matches paramedic allocation, then = No Else missing (including patients with no advanced airways management attempts)

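### A patient known to have died at scene, but with no stop time on Form E1, is coded as missing for 72-hour survival and time to death

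*Protocol*

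**What the plan says.** All the rules are in SAP section 5.4.

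- **Survival status** comes from Form D: "If admitted to ED (Form D)=No, then = Died on scene".
- **Date of death** for these patients: "If survival status=died on scene, then = Date resus stopped (Form E1". **Time of death**: "If survival status=died on scene, then = Time resus stopped (Form E1". Neither rule names another source.
- **Time to death** for patients who die needs both items: "Date of death – Incident date (Form A))*24*60 + (Time of death – Incident time (Form A".
- **The event/censor variable** needs only the status: "If (survival status≠survived to 30 days/hospital discharge & survival status≠missing) or has patient died since hospital discharge=Yes, then = 0". The value 0 means died.
- **72-hour survival** is scored No by this line: "if time to death<72 hours & time to death censor variable=0, then = No". The rule closes by setting anything unmatched to missing. The 0-72h time and event variables have the same structure.

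SAP section 6.2.2 says that time to death will be formally compared in place of ICU and hospital stay. Skeleton Table T6 gives 72-hour survival an odds ratio and 0-72h time to death a hazard ratio. Under SAP section 6.2.7, an outcome with less than 5% missing is analysed on complete cases; above 5%, multiple imputation is considered.

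**The concern.** The fact of an on-scene death and its timing come from different forms. Form D can show that the patient died at scene while Form E1 supplies no stop time. The trial then holds the answer to the 72-hour question but records it as unknown, and has a death that cannot enter the time-to-event models.

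The SAP itself allows for missing E1 items. One deviation rule tests "Paramedic AIRWAYS-2 ID (Form E1) ≠ missing". Section 4 lists Form B after Form E1 for presenting rhythm, witness status and bystander CPR. The time-of-death rule gives a default of midnight to two other groups of deaths whose clock time is not collected. On-scene deaths have neither a fallback nor a default, and the stop time is not in the section 4 list of variables with more than one source.

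The loss depends on the outcome, because only deaths can be lost by this route. Complete-case survival can therefore only move upwards.

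**Working it through.** The plan states no figure on this point to reproduce. The check has two parts.

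**1. The rules traced for one on-scene death**

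| Variable | E1 stop time present (example 0.75 h) | E1 stop time absent |
|---|---|---|
| Survival status (Form D) | Died on scene | Died on scene |
| Time to death | 0.75 h | missing |
| Event/censor variable | 0 (died) | 0 (died) |
| 72-hour survival | No | missing |
| Time to death 0-72h | 0.75 h | missing |
| Event variable 0-72h | 0 (died) | missing |

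The right-hand column contradicts itself: the overall event variable says died, while the 72-hour variables say unknown.

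**2. Size under complete-case analysis**

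Inputs:
- N = 9,070 (protocol section 4.7).
- s, the share dying at scene, is not given. Assumed 50-60%.
- S, true 72-hour survival, is not given. Assumed 10-20%. Protocol section 4.6.2 expects about 20% to survive to hospital admission and 9% to discharge, so this range is plausible.
- m, the share of on-scene deaths without a stop time, is not given. Results are per 1%.

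Deaths lost = N × s × m:
- 9,070 × 0.50 × 0.01 = 45
- 9,070 × 0.60 × 0.01 = 54

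Observed survival = N × S / (N − deaths lost):
- S = 10%, s = 50%: 907 / 9,025 = 10.05%, a rise of 0.05 points
- S = 20%, s = 60%: 1,814 / 9,016 = 20.12%, a rise of 0.12 points

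Equivalently, observed survival = S / (1 − s × m). Widening s to 40-80% gives 0.10 / 0.996 = 10.04% and 0.20 / 0.992 = 20.16%, so rises of 0.04 to 0.16 points.

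For a larger loss, take m = 5%. Overall missingness from this route is s × m = 2.5-3.0%, still below the 5% threshold, so complete-case analysis still applies. Observed survival becomes 0.10 / 0.975 = 10.26% or 0.20 / 0.970 = 20.62%, rises of 0.26 and 0.62 points.

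**Effect on the comparison.** The observed odds in an arm are S / (1 − S − s × m). If S, s and m are equal in the two arms, the odds are equal and the odds ratio stays at 1.00.

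**The case against.** Several points on the other side are sound.

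- **Late forms are chased.** Protocol section 5.6.2 says "Occasionally the participating paramedic will not complete the form immediately, in which case" the research paramedic contacts the paramedic and supports completion. If that fails, relevant data can be taken from the routine ambulance record. SAP section 3.4 says that a CRF is also requested for patients who were not consciously enrolled. The feasibility study reported complete data sets for more than 95% of patients (protocol section 2.1). The number affected may therefore be small. This limits the size but does not repair the rule, because no derivation says that a stop time found elsewhere replaces the E1 item.
- **General safeguards exist.** SAP section 6.2.7 footnotes missing data and explores the reasons if missingness differs substantially between groups. Table T6 shows on-scene deaths beside 72-hour survival, so a shortfall would be visible. It would still not be corrected, and imputation above 5% would impute a status already known.
- **The primary outcome is untouched.** Under SAP section 5.1, patients who do not survive receive mRS 6 without needing a date.

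Two stronger readings are tempting, and the documents support neither.

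- A reader might infer that software ranking missing values above any number would pass these deaths through the 72-hours-or-more line and code them as survivors. The rule's own last line sends an unmatched record to missing, so that coding would depart from the SAP. The SAP mentions Stata only as an example for imputation.
- A reader might infer bias between arms, because unblinded paramedics complete Form E1. As a pure illustration, 2% against 6% missing with S = 15% and s = 60% gives 0.15 / 0.988 = 15.18% against 0.15 / 0.964 = 15.56%, an odds ratio of about 1.03. Nothing in the documents indicates that missingness differs by arm.

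**Conclusion.** The gap is real and minor. As written, SAP section 5.4 turns a known on-scene death into a missing value for 72-hour survival and for both 0-72h variables when the E1 stop date or time is absent. It also removes that death from the overall time-to-death analysis.

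The consequence is a slight overstatement of 72-hour survival, about 0.05 to 0.12 percentage points per 1% of on-scene deaths affected. That figure rests on the assumed 50-60% dying at scene and 10-20% alive at 72 hours, and on complete-case analysis. The documents do not say how often the stop time is missing, so the total effect cannot be fixed. With equal missingness the treatment comparison is essentially unchanged. The case for correcting the rule is that 72-hour status is already known for these patients and need not be lost.

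**What to change.** 1. Set 72-hour survival to No and the 0-72h event variable to 0 (died) whenever survival status is 'Died on scene', whether or not a time is recorded. This needs one SAP line and a small change to the derivation code, using data already held.

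2. For time to death, overall and 0-72h, state what replaces a missing stop date or time. Either set a default, as the SAP already does for other deaths, or use the routine ambulance record where the stop time is already held. The midnight value itself should not be carried over without thought: read as the start of the incident date, it would precede the incident and give a negative time.

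3. Footnote, by arm, how many records use the substitute.

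The default costs nothing beyond code. The ambulance-record route is free only where the stop time has already been extracted. SAP section 4 lists no second source for it, so returning to the records could mean additional extraction.

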1916 intervals (95% CI). .

1917 • **Continuous outcomes** will be summarised by means and SDs in each treatment group, if distributions
1918 are approximately normal. If distributions are non-normal data will be summarised by the median and
1919 IQR or geometric mean (GM) if a logarithmic transformation provides an approximately normal
1920 distribution. Outcomes will be compared using linear regression. For untransformed data treatment
1921 comparisons will be presented as adjusted differences in means with 95% CI, and for logarithmically
1922 transformed data as adjusted ratios of GMs with 95% CI. Due to the large numbers of trial patients not
1923 expected to survive to 30 days/hospital discharge, a two-part zero-inflated modelling approach will also
1924 be considered for EQ5D visual analogue scale and summary index scores. This will comprise a) an
1925 occurrence model, a logistic regression model for the occurrence of death vs survival; b) intensity model,
1926 a log-linear model for the score, conditional on survival. If it is not possible to fit the model, then an
1927 analysis restricted to those who survive to hospital discharge will be considered.

1928 • **Time to event outcome** time to death will be summarised by the median and IQR in each intervention
1929 group. This will be compared using Cox's proportional hazards or parametric models as appropriate. The
1930 choice of model to use will depend on the distribution of the data. The intervention comparison will be
1931 presented as a hazard ratio (HR) and 95% CI if a proportional hazards model is used or time ratios (TR)
1932 and 95% CI if an accelerated failure time (AFT) model is used. Times will be censored at last contact for
1933 patients known to be alive at that time.

1934 • **Longitudinal outcomes** will be summarised for each time point. Binary and continuous outcomes will
1935 be compared using logistic and linear mixed effects methodologies respectively, with the treatment group
1936 and study design variables (see section 6.2.1) fitted as fixed effects, and patient terms as random effects.
1937 If a time x treatment interaction is not statistically significant at the 10% level an overall treatment effect
1938 will be reported. If the interaction is statistically significant the changes in treatment effect with time will
1939 be described. Different variance/covariance structures will be explored, and the structure that provides

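### Time to death: a non-consenting patient who dies after ICU discharge is an event on the date of death, but one who survives is censored back at ICU discharge

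*Protocol*

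**What the plan says.** All of this is in the SAP.

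- **Deaths (5.4, Time to death and Date of death).** The time runs to the date of death "For patients who die prior to admission, in hospital, or during the follow up period". For deaths on the ward after ICU the date rule is: "If survival status=died prior to hospital discharge & consent status≠active & consent status≠passive, then = death2 date (Form W2". For deaths after discharge it is: "If survival status=survived to 30 days/hospital discharge & has patient died since hospital discharge=Yes, then = death3 date (Form W2". This last rule has no consent condition.
- **Survivors (5.4, Time to death).** Those who "did not consent to active or passive follow-up (i.e. censored at ICU discharge for analysis" stop at ICU discharge. Passive consenters, and patients who "consented to active follow-up but do not provide any 3 or 6 month data (i.e. censored at hospital discharge for analysis", stop at hospital discharge.
- **General rule (6.2.2).** "Times will be censored at last contact for" patients known to be alive then.
- **Data held (3.1).** The mRS at hospital discharge is kept for every patient, consenting or not.
- **72-hour variables (5.4).** An mRS other than 6, dated more than three days after the incident, counts as proof of survival to 72 hours.
- **Survivor status (5.4).** A patient admitted to ED "and survived to ICU admission (Form G)=No, then = Died prior to ICU admission". Every route to the survivor category requires ICU admission to be Yes.

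**The concern.** Take two patients who leave ICU alive and give neither active nor passive consent. One dies on the ward and is an event on that day. The other goes home and is removed from the risk set on the day of ICU discharge. The second patient falls under that censoring rule only because survival to discharge or 30 days is already known. The censoring time therefore depends on the outcome. It always takes survivors out and never deaths, so the later risk sets are too small and mortality after ICU is overstated.

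Time to death is not a minor variable: 6.2.2 says it is formally compared in place of length of ICU and hospital stay, and it appears in Table T6 beside the primary outcome. Sections 5.4 and 6.2.2 would also lead two programmers to different datasets.

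**Working it through.** **1. The rules side by side**

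| Patient | Later outcome | Treatment in 5.4 |
|---|---|---|
| Left ICU, neither consent | Dies on ward | Event on date of death |
| Left ICU, neither consent | Alive at discharge/30 days | Censored at ICU discharge |
| Passive, or active with no questionnaire | Dies after discharge, on Form W2 | Event on date of death |
| Passive, or active with no questionnaire | Alive | Censored at hospital discharge |

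Consent limits do not explain the second row, because the mRS is retained for all and its date is already used for the 72-hour variables.

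**2. Scale.** The documents give no figure for time to death to reproduce. Inputs: 9,070 patients (protocol 4.7), 9% surviving to discharge (4.6.2), and 86% of discharged patients consenting to follow-up in the feasibility study (5.12). Survivors: 0.09 × 9,070 = 816. If the other 14% refused both options (an assumption): 0.14 × 816 = 114.

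**3. Between ICU and hospital discharge.** Let S_icu be the share of enrolled patients leaving ICU alive (not stated; 9.5% to 12% assumed), S_dis = 9%, and r the share of survivors censored at ICU discharge. Kaplan-Meier survival at discharge is

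S_icu × [1 − (S_icu − S_dis) / (S_icu − r × S_dis)].

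With S_icu = 10% and r = 14%: 0.10 × [1 − 0.01 / (0.10 − 0.0126)] = 8.86%, against a true 9.00%. The ward death risk reads 0.01 / 0.0874 = 11.4% instead of 10.0%.

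| S_icu | KM survival, r = 14% | Understated by (points) |
|---|---|---|
| 9.5% | 8.92% | 0.08 |
| 10% | 8.86% | 0.14 |
| 11% | 8.74% | 0.26 |
| 12% | 8.65% | 0.35 |

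With r from 5% to 25%, the range is 0.03 to 0.69 points.

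**4. After hospital discharge.** Let q be the share of survivors dying by 6 months (3% to 6% assumed) and f the share of those staying alive who are followed (40% to 86% assumed), with every death found. KM survival is 9% × [1 − q / (q + (1 − q) × f)].
- q = 3%, f = 86%: 8.69% against a true 8.73%, 0.04 points low.
- q = 6%, f = 40%: 7.76% against a true 8.46%, 0.70 points low.

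**5. Both parts together.** Simulation: 200 runs, 4,535 per arm, 9% survival to discharge, 10% leaving ICU alive, 4% dying after discharge, 14% non-consent, all deaths found, unadjusted Cox model.

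| Share of other survivors followed | 30-day survival, true / SAP rule | 6-month survival, true / SAP rule |
|---|---|---|
| 86% | 9.01% / 8.66% | 8.67% / 8.23% |
| 50% | 8.96% / 8.42% | 8.62% / 7.73% |

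The hazard ratio was 1.0014 with full follow-up and 1.0015 under the SAP rule. With 8% v 10% survival it was 0.9405 under both. With 10% v 20% non-consent by arm (60% of the others followed) it was 0.998 with full follow-up and 1.001 under the SAP rule.

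**6. Median and IQR.** Protocol 4.6.2 expects 20% to survive to admission, so about 80% die before it. No censoring in 5.4 precedes ICU discharge. The 25th, 50th and 75th percentiles of time to death are therefore reached before anyone is censored.

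**The case against.** The strongest reply is that almost nothing reported will move. Section 6.2.2 and Table T6 present a median with IQR and a hazard or time ratio, not a 6-month survival percentage. Steps 5 and 6 bear this out, and the point stands.

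A reader might infer that mortality is overstated up to twofold. With 5% true mortality after discharge and 80%, 65% or 50% of survivors followed, 5 / (5 + 95 × f) gives 6.2%, 7.5% or 9.5%, or 1.2 to 1.9 times the truth. But that describes only patients already discharged alive, about 9% of the cohort. In all trial patients, mortality would read 91 + 9 × 0.062 = 91.56% to 91.86%, against 91 + 9 × 0.05 = 91.45%. Protocol 6.1 also expects complete follow-up of consenting patients, so the low response rates are pessimistic.

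Three further replies have force:
- For an active consenter who returns nothing, hospital discharge may well be the last contact. That rule need not conflict with 6.2.2; only the non-consenter rule does.
- The 114 is not established. The 86% refers to consent at 3 months in the feasibility study, and some of the remaining 14% might choose passive follow-up here.
- It is unclear whether Form W2 records post-discharge deaths outside active follow-up. The ward asymmetry does not depend on this.

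On survivor status, a reader might infer that survivors treated in CCU will be coded as dead. The documents do not show this: protocol 5.6 treats ICU and CCU as one stage, and the Form G coding is not given.

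**Conclusion.** The rule is wrong as written, but its consequence is small. Section 5.4 censors non-consenting survivors earlier than they are known to be alive while counting deaths in the same consent group, and it disagrees with 6.2.2. The result is an understatement of whole-cohort survival of about 0.1 to 0.9 points in the main scenarios. This rests on assumed ICU survival, consent, response and late mortality, and on all deaths being found. The relative error is larger for mortality after ICU alone.

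The documents do not support a claim that the treatment comparison is materially biased: the hazard ratio shifted by only about 0.003 even with non-consent twice as common in one arm. The primary outcome does not use this variable, and the mRS-date rule covers most of the 72-hour problem.

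The ICU-only route to survivor status is a separate coding fault on a literal reading. A survivor with ICU admission = No would be flagged as a death with no date of death. How often this could happen cannot be judged from the documents.

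**What to change.** - Censor non-consenting survivors at the discharge or 30-day mRS date, or at the hospital discharge date where no mRS date is available. Section 5.4 sets the incident-to-mRS interval to missing unless mRS was measured face to face, so check that one of the two dates is held for each such patient.
- Count later deaths as events only in patients whose vital status is ascertained over the same window. Otherwise censor at the end of that window. The documents show no date-last-known-alive field on Form W2, so censoring everyone at day 183 cannot be assumed possible.
- Let mRS not equal to 6, or survival to discharge, define a survivor whatever the ICU admission field says.
- State the rule once, so that 5.4 and 6.2.2 agree.

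In the 86%-followed simulation (true 6-month survival 8.67%, SAP rule 8.23%), the first change alone gives 8.45% and the first two together 8.57%. A small bias remains because discharge is itself an informative time to stop; truncating the analysis at discharge/30 days for everyone is an alternative. The cost is revised derivation code and the loss of a few late deaths from the event count.
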